7.9.2.2 Secondary Endpoints

All sensor data collected during the 6 month study period and 6 month continuation phase will be used to perform all statistical test mentioned below. Descriptive summaries of all outcomes mentioned below generated with all 6 month SG data in continuation phase will be provided as well.

7.9.2.2.1 Percentage of Time in Range (70-180 mg/dL), in Hyperglycemia (> 180 mg/dL, > 250 mg/dL) and Hypoglycemia (< 54 mg/dL, < 70 mg/dL)

Percentage of time spent within range with sensor glucose (SG) between 70 - 180 mg/dL (3.9-10.0 mmol/L), in hyperglycemic range with SG > 180 mg/dL (> 10.0 mmol/L), > 250 mg/dL (13.9 mmol/L) and in hypoglycemic range with SG < 54 mg/dL (3.0 mmol/L), < 70 mg/dL (3.9 mmol/L) will be computed using the sensor data collected during 6 months from each period will be used for analysis.

The percentage of time spent within range (70-180 mg/dL) for subject i at period j will be calculated as:

$$\frac{\text{Total number of sensor reading with SG between } 70 - 180 \text{ mg/dL for subject i at period j}}{\text{Total number of sensor readings for subject i at period j}}$$

The percentage of time spent in hyperglycemic range > 180 mg/dL or > 250 mg/dL for subject i at period j will be calculated as:

$$\frac{\text{Total number of sensor reading with SG } > 180 \text{ or } > 250 \text{ mg/dL for subject i at period j}}{\text{Total number of sensor readings for subject i at period j}}$$

Similarly, the percentage of time spent in hypoglycemic range < 54 mg/dL or < 70 mg/dL for subject i at period j will be calculated as:

$$\frac{\text{Total number of sensor reading with SG } < 54 \text{ or } < 70 \text{ mg/dL for subject i at period j}}{\text{Total number of sensor readings for subject i at period j}}$$

The within group difference of Time in specific range (70-180, <54, <70, >180, >250 mg/dL) between study period and continuation phase will be compared using paired t test if normality assumption is met, Wilcoxon signed rank test if normality assumption is rejected.

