
Visit 6A: CGM Start [Visit 5A + 7 days (Window + 7 days)]
 
This visit can be done remotely or onsite.
 
Site staff will:
 
▪ Upload the AHCL into CareLink, if visit is onsite. Use correct Subject ID (327-XXX-XXX).▪ Ensure CareLink upload was done/Advise and (re)train subject to perform weekly CareLink uploads▪ Review AHCL therapy / Adjust settings.▪ Retrain subject on Pump therapy as needed.▪ Start CGM with AHCL (in Manual Mode) and subject stops FGM/RT-CGM.▪ Review adverse event or device deficiency, if any. 
If visit is onsite:
 
▪ Dispense supplies to subject (indicative quantity for 3 months):
○ 1 Guardian Link 3 Transmitter kit○ 20 sensors○ 750 strips○ 30 Infusion sets (3 boxes of 10)○ 30 Reservoirs (3 boxes of 10)○ 12 AA batteries (3 packs of 4)	
Visit 6A: Follow-up call [Visit 5 + 14 days (Window ± 5 days)]
 
Study staff will call the subject:
 
▪ Review therapy / Adjust settings.▪ Review adverse event or device deficiency, if any.

Treatment Arm	Control Arm

Visit 6B [Visit 6A + 3 days (Window \pm 1 day)]
 
This visit can be done by phone or onsite.
 
Site staff will:
 
▪ Ensure CareLink upload was done/Advise subject to perform weekly CareLink uploads.▪ Review AHCL therapy / Adjust settings.▪ Retrain subject on Pump/CGM therapy as needed.▪ Review adverse event or device deficiency, if any. 
If the visit is conducted onsite, site staff will additionally:
 
▪ Upload AHCL into CareLink. Use correct Subject ID (327-XXX-XXX).	

Treatment Arm	Control Arm

Visit 6C: Auto Mode Start [Visit 6A + 7 days (Window -1 /+ 7 days)]
 
This visit can be done by phone or onsite.
 
Site staff will:
 
▪ Ensure CareLink upload was done/Advise subject to perform weekly CareLink uploads.▪ Review AHCL therapy / Adjust settings.▪ Retrain subject on Pump/CGM as needed.▪ Site staff/Subject to start Auto Mode on AHCL.▪ Review adverse event or device deficiency, if any. 
If the visit is conducted onsite, site staff will additionally:
 
▪ Upload AHCL into CareLink. Use correct Subject ID (327-XXX-XXX).	

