9.8.1.3. Sensor Glucose Values

At baseline during the run-in phase and in the control arm during the study phase, SG data will be collected using the blinded CGM. Refer to Blinded CGM instructions and section 7.4 for more details.

In the treatment arm, SG data will be collected by subject's study pump and calibrated by subject's CONTOUR®NEXT LINK 2.4 study meter.

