4.1.2 Objective for Treatment Group

The primary objective is to confirm the long-term benefits of AHCL therapy. The non-inferiority on glycemic control of the AHCL system in continuation phase versus in study period will be tested.

5. Investigation Plan

This study is a pre-market, multi-center, prospective, open label, adaptative, confirmatory, randomized controlled trial in insulin-requiring adult subjects with type 1 diabetes on MDI therapy. The study period for each subject will be approximately 13 months.

Figure 1: Study Design

The study consists of two separate cohorts, Cohort A with subjects on MDI + FGM (confirmatory part of the study) and Cohort B with Subjects on MDI + Real-Time CGM (exploratory part of the study). Each cohort will have a separate randomization.

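### The treatment group's sensor durability tests count the Manual Mode training days in the study-period reference, which modestly favours non-inferiority for three of five endpoints

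*SAP*

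**What the plan says.** SAP 4.1.2 states the aim for the treatment group: "The non-inferiority on glycemic control of the AHCL system in continuation phase versus in study period will be tested". SAP 7.5.2 turns this into a fixed sequence of six non-inferiority tests: HbA1c first, then time above 250, above 180 and within 70-180 mg/dL (margin 6 points each), below 54 (2 points) and below 70 mg/dL (5 points).

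For the five sensor tests, SAP 7.9.2.2 says "All sensor data collected during the 6 month study period and 6 month continuation phase will be used", and adds that the percentages "will be computed using the sensor data collected during 6 months from each period will be used for analysis". Each percentage is the number of qualifying readings divided by all readings for that subject and period, so every reading has the same weight. Neither document gives a start date for these data or leaves out the training period.

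Protocol 9.8.1.3 gives the source of the readings: "In the treatment arm, SG data will be collected by subject's study pump". Protocol 9.3 gives the timing. CGM begins at "Visit 6A: CGM Start [Visit 5A + 7 days (Window + 7 days", where staff are to "Start CGM with AHCL (in Manual Mode) and subject stops FGM/RT-CGM". The closed loop follows at "Visit 6C: Auto Mode Start [Visit 6A + 7 days (Window -1 /+ 7 days". All of these visits lie inside the study phase. In the continuation phase, this arm's Visits 10 and 11 are follow-up calls on unchanged therapy (Protocol 9.4).

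The rule differs elsewhere. The control-group tests (SAP 7.9.1.2) use 2-week windows at 3 and 6 months against 9 and 12 months. Protocol 13.7 also describes sensor comparison over two weeks at 3 and 6 months.

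**The concern.** The test asks whether control achieved in the study period is kept in the continuation phase. The study-period reference contains 6 to 14 days per subject in which new pump users ran in Manual Mode, and the continuation data contain no such block. Protocol 9.8.2 asks subjects to stay in Auto Mode as much as possible so that time in range is as high as possible. On that premise the lead-in makes the reference look worse: time in range is lower, and time above 180 and above 250 mg/dL is higher. In a non-inferiority test a worse reference helps the conclusion, so part of each 6-point margin at steps 2 to 4 is spent before like is compared with like. A real loss of control close to the margin would then pass too often.

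**Working it through.** The plan gives no figure to reproduce for these tests, because SAP section 6 states that no power analysis was done for this phase. The group size used below, 32 per arm, comes from SAP 6.2. It does reproduce there: a difference of 0.5, SD 0.7 and two-sided 0.05 give t-test power 0.803.

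**Inputs from the documents**
- Visit 6A: Visit 5A + 7 days, up to 7 days later. Visit 6C: Visit 6A + 7 days, window -1 to +7, hence 6 to 14 Manual Mode days.
- Visit 7A: Visit 5A + 3 months, ±10 days. Visit 8: Visit 7A + 3 months, ±10 days. Visit 9: Visit 8 + 14 days, up to 7 days later.
- Margin of 6 points (SAP 7.5.2). Two-sided 0.05 (SAP 7.2), taken as one-sided 0.025 for non-inferiority.

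**Assumptions not in the documents**
- D, the amount by which Manual Mode time in range lies below that after Visit 6C: 10 or 20 points.
- SD of the paired change in time in range: 8 points, with 6 and 10 as variants. N = 32.

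**Step 1: lead-in share.** f = Manual Mode days / sensor days, with 6 months = 182.6 days from Visit 5A.
- Target dates, ending at Visit 8: 7 / (182.6 - 7) = 7 / 175.6 = 4.0%.
- Target dates, ending at Visit 9: 7 / (182.6 + 14 - 7) = 7 / 189.6 = 3.7%.
- Smallest: 6 / (182.6 + 20 + 21 - 7) = 6 / 216.6 = 2.8%.
- Largest: 14 / (182.6 - 20 - 14) = 14 / 148.6 = 9.4%. This has late Visits 6A and 6C, early Visits 7A and 8, and data ending at Visit 8.

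**Step 2: shift in the reference.** Shift = f × D.
- f = 3.7%: 0.37 points (D = 10) or 0.74 points (D = 20).
- f = 4.0%: 0.40 or 0.80 points, which is 7% or 13% of the margin. The effective margin becomes 6.4 or 6.8.
- f = 9.4%: 0.94 or 1.88 points, but only if every subject sits at those window limits.

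**Step 3: false non-inferiority.** At a true 6-point loss against Auto-Mode-period data, the chance of passing is Φ(-1.96 + f·D / (SD/√32)). With SD 8 the standard error is 8/√32 = 1.414.
- D = 10: Φ(-1.96 + 0.40/1.414) = 0.047.
- D = 20: Φ(-1.96 + 0.80/1.414) = 0.082.
- The nominal value is 0.025. With SD 10 the results are 0.041 and 0.066; with SD 6 they are 0.057 and 0.114.

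**Step 4: no true change.** Power = Φ((6 + f·D)/1.414 - 1.96). This is 0.989 without the lead-in, and 0.995 (D = 10) or 0.998 (D = 20) with it.

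**Direction by endpoint.** The protocol's premise covers time in range and, by implication, high glucose. Neither document says whether Manual Mode gives more or less time below 54 or 70 mg/dL, so no direction can be assigned to steps 5 and 6. Step 1 compares HbA1c at Visits 8 and 13 and uses no sensor data.

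**The case against.** The strongest reply is that Manual Mode is part of the AHCL system. The pump starts at Visit 5A, and SAP 7.9.2.3.5 divides Manual Mode time by total time on AHCL therapy. Protocol 7.2 describes suspend functions available in Manual Mode, and the Auto Mode target is only at least 85% of the time, so the continuation phase contains Manual Mode as well. This stands against a reading that a reader might be tempted to make, namely that the reference is a different treatment recorded before AHCL was switched on. The documents do not support that: both periods are mixtures, and what begins at Visit 6C is Auto Mode. If D is taken as the pure Manual-to-Auto difference and later data are 85% Auto Mode, the shifts of 0.4 and 0.8 fall to 0.85 × 0.4 = 0.34 and 0.85 × 0.8 = 0.68 points. The uneven training block remains.

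Second, the SAP also speaks of six months of data per period. Six months counted back from Visit 9 would begin 14 days after Visit 5A, which is the nominal Visit 6C, and would contain almost no lead-in. But the SAP does not state that rule, and its instruction to use all the data points the other way.

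Third, the tests are labelled exploratory, were not powered, and follow an HbA1c test that is unaffected. That limits the consequence. It does not justify an avoidable tilt in a sequence that the SAP presents as controlling multiplicity.

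**Conclusion.** The point holds, at modest size. As written, the rule puts 6 to 14 Manual Mode training days into the study-period reference and nothing comparable into the continuation phase. On the protocol's own premise this favours non-inferiority for time above 250, above 180 and within 70-180 mg/dL. The share is about 3.7% to 4.0% of sensor days at target dates, and about 3% to 9% at the window extremes. The shift of about 0.4 to 0.8 points rests on an assumed 10 to 20 point difference, and the error rates also rest on an assumed SD.

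Two stronger inferences are not supported. The lead-in does not decide the result: at target dates D would have to be about 6 / 0.040 = 150 points to use up the margin, which is impossible, and a truly maintained effect passes almost equally often either way. Nor are all five sensor endpoints shown to be biased in the same direction, since that is unknown for the two hypoglycaemia tests. The matter is worth correcting because a near-margin result could turn on it.

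**What to change.** In SAP 7.9.2.2, and for the sensor endpoints of the treatment group in 7.9.2.3, define the windows by one of two rules:

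- Study-period data run from Auto Mode start (Visit 6C) to Visit 9, and continuation data from after Visit 9 to Visit 13. Tying the start to the Visit 6C date keeps the rule independent of how much Auto Mode a subject later uses.
- Or use the 2-week windows at 3 and 6 months and at 9 and 12 months already set for the control group, which makes the two groups consistent.

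Keep the all-data version as a sensitivity or descriptive analysis.

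The cost is one sentence and a date filter. The first rule drops 1 to 2 of about 27 weeks of study-period data (190 / 7 = 27). The second leaves four weeks per period. Under either, the non-inferiority result becomes slightly less favourable. No visit or treatment procedure changes.

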7.9.2.3 Ancillary Endpoints

Non-inferiority test will be applied to ancillary endpoints if needed.

7.9.2.3.1 Number of Biochemical Hypoglycemic events

A biochemical hypoglycemic event with SG < 54 mg/dL is defined as sensor glucose values less than 54 mg/dL (3.0 mmol/L) for 15 or more consecutive minutes. A biochemical hypoglycemic event with SG < 70 mg/dL is defined as sensor glucose values less than 70 mg/dL (3.9 mmol/L) for more than 20 consecutive minutes. When the time between two successive events is less than 30 minutes, they will be combined and counted as one event. The mean number of biochemical hypoglycemic events with SG < 54 mg/dL (3.0 mmol/L), < 70 mg/dL (3.9 mmol/L) per subject per week based on 15 and 20 consecutive minutes will be computed using the sensor data collected during each of the 2 periods of 6 months. The mean number of hypoglycemic events (MNHE) per week at each period for each subject will be calculated as:

$$\frac{\text{number of biochemical hypoglycemic event for subject i at period j}}{\text{duration of sensor wear for subject i at period j in weeks}}$$

Where the duration of sensor wear for subject i at period j is the number of sensor readings (capped at 4032) for subject i at period j divided by 2016. Mean number of biochemical hypoglycemic events with SG < 54 mg/dL (3.0 mmol/L) based on 20 minutes definition and < 70 mg/dL (3.9 mmol/L) per week based on 15 minutes definition will be analyzed and reported as additional analyses. Analysis on mean number of biochemical hypoglycemic events with SG < 54 mg/dL (3.0 mmol/L) (based on 15 minutes) will be using non-inferiority test with non-inferiority margin of 35% of the observed mean in the control group.

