7.9.1.3.1 Number of Biochemical Hypoglycemic events

A biochemical hypoglycemic event with SG < 54 mg/dL is defined as sensor glucose values less than 54 mg/dL (3.0 mmol/L) for 15 or more consecutive minutes. A biochemical hypoglycemic event with SG < 70 mg/dL is defined as sensor glucose values less than 70 mg/dL (3.9 mmol/L) for more than 20 consecutive minutes. When the time between two successive events is less than 30 minutes, they will be combined and counted as one event. The mean number of biochemical hypoglycemic events with SG < 54 mg/dL (3.0 mmol/L), < 70 mg/dL (3.9 mmol/L) per subject per week based on 15 and 20 consecutive minutes will be computed using the sensor data collected during each of the 2 periods of 2 weeks. The last 4032 sensor readings (2 weeks) from each period will be used for analysis. The mean number of hypoglycemic events (MNHE) per week at each period for each subject will be calculated as:

$$\frac{\text{number of biochemical hypoglycemic event for subject } i \text{ at period } j}{\text{duration of sensor wear for subject } i \text{ at period } j \text{ in weeks}}$$

Where the duration of sensor wear for subject *i* at period *j* is the number of sensor readings (capped at 4032) for subject *i* at period *j* divided by 2016. Mean number of biochemical hypoglycemic events with SG < 54 mg/dL (3.0 mmol/L) based on 20 minutes definition and < 70 mg/dL (3.9 mmol/L) per week based on 15 minutes definition will be analyzed and reported as additional analyses. Analysis on mean number of biochemical hypoglycemic events with SG < 54 mg/dL (3.0 mmol/L) (based on 15 minutes) will be using non-inferiority test with non-inferiority margin of 35% of the observed mean in the control group.

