7.9.2.3.2 Mean of Sensor glucose Values and GMI

Mean number of sensor glucose (SG) in mg/dL and GMI will be analyzed and reported. The mean SG and GMI for a subject at period j will be calculated as the overall mean of the SG and GMI values.

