7.9.2.3.4 Amplitude of Glycemic Excursions (MAGE)

The excursion amplitudes of the glucose values measured by mean amplitude of glycemic excursions (MAGE) will be calculated for two periods using the 6 months sensor glucose data. Analysis will be performed and reported.

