7.9.2.3.6 Percentage of Sensor Use for Continuation Phase

Descriptive statistics for the percentage of sensor use during the 6 months (After visit 9 to visit 13) continuation phase will be reported.

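### The treatment-group weekly hypoglycaemia rate counts events over 6 months but divides by at most 2 weeks of wear, so for almost any subject it is a raw count halved

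*SAP*

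**What the plan says.** For the treatment group, SAP 7.9.2.3.1 states that the weekly number of events (below 54 and below 70 mg/dL) "will be computed using the sensor data collected during each of the 2 periods of 6 months". The rate is events divided by duration of sensor wear in weeks, and that duration "is the number of sensor readings (capped at 4032) for subject i at period j divided by 2016".

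The control-group section, 7.9.1.3.1, uses the same denominator but a different data window: "The last 4032 sensor readings (2 weeks) from each period will be used for analysis". There, numerator and denominator cover the same 2 weeks.

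The other treatment-group sensor outcomes carry no cap:

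- The secondary endpoints (7.9.2.2): "All sensor data collected during the 6 month study period and 6 month continuation phase will be used to perform all statistical test".
- Mean sensor glucose (7.9.2.3.2): "will be calculated as the overall mean of the SG and GMI values".
- SD (7.9.2.3.3): taken over all readings in the period.
- MAGE (7.9.2.3.4): "will be calculated for two periods using the 6 months sensor glucose data".

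The two phases are compared within subject by paired t-test or Wilcoxon signed rank test (SAP 7.2). For events below 54 mg/dL (15-minute definition), 7.9.2.3.1 plans a non-inferiority test with a "non-inferiority margin of 35% of the observed mean in the control group". Under SAP 7.5.2, tests on ancillary endpoints are optional and their p-values may not be claimed.

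**The concern.** The treatment-group text replaces the 2-week window with 6 months but keeps the 2-week cap on wear time. The numerator then spans about 26 weeks and the denominator at most 2. Two things follow.

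- **Level.** The reported events per week on AHCL would be several times the true weekly rate. Readers are likely to take this figure at face value and to set it beside the correctly scaled control-group rate.
- **Comparison.** Once the cap binds in both phases, the denominator is the constant 2. The rate is then no longer adjusted for wear or for the length of the data window. A subject who wears the sensor less in the continuation phase appears to have less hypoglycaemia, whatever the true rate.

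**Working it through.** **Inputs.** Protocol 13.7 gives 288 sensor values per day, which agrees with one reading every 5 minutes (SAP 3.1). Visit targets for the treatment arm are in Protocol 9.3 and 9.4. SAP 7.9.2.3.6 starts the continuation phase after Visit 9 and ends it at Visit 13. Wear percentages are assumptions; the documents give no expected wear.

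**Reproducing the SAP's own figures.** 288 x 7 = 2016 readings per week and 288 x 14 = 4032 readings in 2 weeks, as 7.9.1.3.1 states. Likewise 288 x 28 = 8064 readings in 4 weeks, as 7.9.1.2.1 states.

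**Formula.** Let E be the events in a period, R the readings, and W = R/2016 the weeks of wear.

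- As written: E / (min(R, 4032)/2016). For R of at least 4032 this is E/2.
- Without the cap: E / (R/2016) = E/W.
- Ratio of the two when W is at least 2: W/2. Below 2 weeks of wear the cap does not bind and the rate is correct.

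**Size over 26 weeks.** Full wear gives 26 x 2016 = 52,416 readings, of which the cap keeps 4032/52,416 = 7.7%. A subject with a true rate of 1.00 per week has 26 events and is reported as 26/2 = 13.0 per week; uncapped, 26/26 = 1.00. At 85% wear the factor is 26 x 0.85 / 2 = 11.05, and at 70% it is 26 x 0.70 / 2 = 9.1.

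**Window length by target dates.** Take Visit 5A as day 0 and 6 months as 182.6 days.

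- Visit 6A (CGM start) is day 7 and Visit 6C (Auto Mode start) is day 14.
- Visit 8 is day 182.6 and Visit 9, 14 days later, is day 196.6.
- Visit 13 is Visit 8 plus 1 + 1 + 1 + 3 months, which is day 365.25.
- Visit 9 to Visit 13 is therefore 168.6 days.

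The SAP does not say where the study-period sensor window starts or ends for this endpoint, so four readings are possible. With an unchanged true rate and equal percentage wear, the apparent change is 168.6 divided by the study-window days, minus 1.

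| Window | Days | Weeks | W/2 at full wear | W/2 at 70% wear | Apparent change |
|---|---|---|---|---|---|
| Visit 6C to Visit 8 | 168.6 | 24.1 | 12.0 | 8.4 | 0% |
| Visit 6A to Visit 8 | 175.6 | 25.1 | 12.5 | 8.8 | -4.0% |
| Visit 6C to Visit 9 | 182.6 | 26.1 | 13.0 | 9.1 | -7.7% |
| Visit 6A to Visit 9 | 189.6 | 27.1 | 13.5 | 9.5 | -11.1% |
| Visit 9 to Visit 13 (continuation) | 168.6 | 24.1 | 12.0 | 8.4 | reference |

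**Effect of wear alone.** With equal windows and an unchanged true rate, a drop in wear from 90% to 70% shows as 0.70/0.90 - 1 = -22%. A rise from 70% to 90% shows as 0.90/0.70 - 1 = +29%.

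**The case against.** The best defence is that this is an evident copy-over from the control-group section. The 6-month wording, the per-week unit and the uncapped neighbouring sections show what was meant. SAP section 8 also requires at least a code review for such endpoints, so a 13-fold rate might well be noticed. That lowers the chance of harm but does not correct the text. SAP 7.12 says the plan will be carried out in full, and a program faithful to the formula would match the document it is reviewed against. The statement in 7.9.2.2 that all sensor data are used sits under secondary endpoints, so for this endpoint it is only indirect evidence of intent.

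A second defence is that the comparison is paired, so the factor W/2 cancels in relative terms when a subject's wear time is the same in both phases. This is right as far as it goes. An inflated level is not by itself a biased comparison; distortion needs a difference in wear or in window length.

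That bears on a stronger reading that a reader might infer: that the visit schedule itself makes the study period longer and so guarantees a spurious fall of 8% to 11%. The documents do not support it. Those figures need the study window to end at Visit 9. Protocol 9.3 does label Visit 9 the end of the study phase, but SAP 7.9.2.1 and 7.9.2.3.7 take the 6-month point at Visit 8. Visit 6C to Visit 8 is exactly as long as Visit 9 to Visit 13, which gives 0%. Nor do the documents show that wear is expected to differ between phases.

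**Conclusion.** The formula in SAP 7.9.2.3.1 is wrong as written, and no other section repairs it. For every treatment-group subject with at least 4032 readings in a phase, the weekly rate is the event count divided by 2. The overstatement is about 8 to 14 times, assuming 70% to 100% wear over 24 to 27 weeks and literal programming of the text.

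The comparison between phases is unprotected against differences in wear or window length. From target dates alone, the supportable apparent change is 0% to about -11%; a difference in window length is possible, not established.

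It would also be too strong to infer that the trial's hypoglycaemia conclusions are at risk. The endpoint is ancillary, all analyses in this SAP are exploratory, and its p-values may not be claimed. The HbA1c and time-in-range tests in the fixed sequence do not use this rate. What is at stake is a wrong descriptive rate and an unreliable exploratory comparison. The text should be fixed before the analysis is programmed.

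**What to change.** In SAP 7.9.2.3.1, delete the parenthesis that caps the readings at 4032, so that wear duration is all readings in the period divided by 2016. This matches the section's own 6-month event count. Restricting the event count to the last 4032 readings, as in 7.9.1.3.1, would also be consistent, but it departs from the 6-month wording. The cost is one wording edit, with no new data.

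Three drafting points can be corrected in the same pass. They do not add to the weight of this one.

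- In 7.9.1.3.1 and 7.9.2.3.1, name the group and the period that supply the mean for the 35% margin. A control-group mean does not fit a test within the treatment group.
- In 7.9.1.3.3 and 7.9.2.3.3, correct the reference to section 7.9.1.2.3, which does not exist in the SAP.
- In the control-group CV, use one set of readings for mean and SD. If the missing reference means 7.9.1.3.2, the mean uses up to 8064 readings and the SD up to 4032.

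With these, the edits touch four subsections.
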